The SEER registry data released as part of SEER-Medicare are included in a customized file known as the SEER-Medicare Cancer file. The information collected on each SEER-reported cancer diagnosis includes patient-level demographic characteristics, date of diagnosis, clinical data about the tumor (e.g., stage, grade, size, ER status, PR status, and HER2 status), and cause and date of death. Linkage with Medicare data provides a database of persons generally aged 65 years and older with detailed information on incident cancer linked with comprehensive longitudinal healthcare utilization data from Medicare *fee-for-service*. In SEER-Medicare, the Medicare date of death information is collected from multiple sources, including the Social Security Administration (SSA), Railroad Retirement Board, and Medicare Common Working File; the Medicare date of death information is known to be complete for the given enrollment year (e.g., 2020 enrollment data will capture deaths occurring in 2020). Because almost all (99%) Medicare deaths are validated (98% through SSA), the vital status information available in the linked SEER-Medicare data make it one of the most authoritative data sources to examine survival outcomes in Medicare beneficiaries with an incident of cancer diagnosis in the US.

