2.1 STUDY DESIGN

[figure not shown]
This study will encompass a retrospective cohort analysis using clinical and administrative claims data from the linked SEER-Medicare database (providing SEER data are available through 2019 and linked Medicare claims are available through 2020) for patients with diagnosis of HR+/HER2- mBC at initial presentation. The study will assess the rates of OS in patients 65 years or older with diagnosis of *de novo* mBC from 2015-2019 who initiated 1L systemic therapy with palbociclib + AI or AI alone following the first approval of palbociclib in February 2015. **Figure 2-1** presents a graphical schema of the study design (drawn for a hypothetical patient and not to scale).

Based on the study schema presented below, the following key study definitions will apply:

- **De novo mBC diagnosis date window:** From 1 February 2015 through 31 December 2019
- **Study index date:** The date of 1L treatment initiation with palbociclib + AI or AI alone after the *de novo* mBC diagnosis
- **Case selection window:** From 1 February 2015 through 30 June 2020 – for the date of 1L treatment initiation (study index date)

- **Baseline period:** The 6-month period before the study index date (to assess patient baseline demographic and clinical characteristics)
- **Study follow-up:** All patients will be followed from their study index date through the earliest of the following: death, disenrollment from Medicare Part A (hospital insurance), Part B (medical insurance), or Part D (prescription drug insurance), enrollment in a health maintenance organization (HMO) plan, or end of the study database (31 December 2020).
- **Overall study period:** From 1 August 2014 (to allow up to 6 months of look back period for any patient with index date in February 2015) through 31 December 2020 (accounting for a minimum 6 months of potential follow-up for any patient with index date in June 2020).

Figure 2-1. Study Design Schematic (Depiction for a Hypothetical Patient)

AI = aromatase inhibitor; HER2- = human epidermal growth factor receptor 2-negative; HR+ = hormone receptor-positive; mBC = metastatic breast cancer.

Note: Figure not drawn to scale.

Study Population

The study population will represent Medicare beneficiaries (men or women) with diagnosis of HR+/HER2- mBC at initial presentation (i.e., de novo), as identified in the SEER-Medicare database.

Data Source

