The SEER registry data released as part of SEER-Medicare are included in a customized file known as the SEER-Medicare Cancer file. The information collected on each SEER-reported cancer diagnosis includes patient-level demographic characteristics, date of diagnosis, clinical data about the tumor (e.g., stage, grade, size, estrogen receptor [ER] status, progesterone receptor [PR] status, and HER2 status), and cause and date of death. Linkage with Medicare data provides a database of persons generally aged 65 years and older with detailed information on incident cancer linked with comprehensive longitudinal healthcare utilization data from Medicare fee-for-service. In SEER-Medicare, the Medicare date of death information is collected from multiple sources, including the Social Security Administration (SSA), Railroad Retirement Board, and Medicare Common Working File; the Medicare date of death information is known to be complete for the given enrollment year (e.g., 2020 enrollment data will capture deaths occurring in 2020). Because almost all (99%) Medicare deaths are validated (98% through SSA), the vital status information available in the linked SEER-Medicare data make it one of the most authoritative data sources to examine survival outcomes in Medicare beneficiaries with an incident of cancer diagnosis in the US.

The linkage of SEER-Medicare data is managed by the National Cancer Institute (NCI), in collaboration with the contributing SEER registries and the Centers for Medicare & Medicaid Services. Investigators must submit a detailed application to the NCI for obtaining access to the required study data, which must be used under the terms of a data use agreement. Based on the most recent data linkage by the NCI, released in December

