4.1 FULL ANALYSIS SET

Inclusion Criteria

Patients must meet all of the following inclusion criteria to be eligible for inclusion in the study:

1. *De novo metastatic (stage IV) disease at initial breast cancer diagnosis during 2015-2019 (Howlader et al., 2018):*
 - *Incident breast cancer diagnosis will be identified using the SEER Site Recode 26000, which includes cases classified as “breast” according to the International Classification of Diseases for Oncology, 3rd Edition codes: C50.0-C50.9, excluding histology codes 9050-9055, 9140, and 9590-9992 (National Cancer Institute, 2023b).*
 - *Staging at diagnosis will be determined using criteria applicable during the specific period. Specifically, the American Joint Committee on Cancer (AJCC) staging 7th edition variable will be used to classify diagnoses in year 2015, the derived SEER combined stage group variable will be used to classify diagnoses in years 2016-2017, and the derived Extent of Disease (EOD) stage group variable will be used to classify diagnoses in years 2018-2019.*
2. *Age \geq 65 years at diagnosis*
3. *“Age” as the reason for Medicare entitlement*
4. *Breast cancer recorded as the first cancer (coded as tumor sequence “1”) or the only cancer (coded as tumor sequence “0”) confirming no evidence of another, previous primary cancer diagnosis.*
5. *HR+/HER2- molecular subtype at diagnosis, using the SEER breast subtype variable (defined according to ER/PR and HER2 status)*
6. *Initiated 1L systemic therapy with a CDK4/6 inhibitor + AI or AI alone*
 - *Subsequently, and differing from Goyal et al. (2023), to assess the primary objective, the study cohort will be restricted to patients initiating 1L therapy with palbociclib + AI or AI alone within 6 months of mBC diagnosis:*
 - *It is assumed that most patients will initiate a systemic treatment within a few months of the diagnosis, and those who did not receive treatment*

PFIZER CONFIDENTIAL

within 6 months may have meaningful unobserved characteristics that likely influenced their treatment decisions.

7. *To ensure complete data for identifying the 1L of therapy, patients will be required to have continuous enrollment in Medicare Parts A and B and have prescription drug coverage (Part D) with no HMO participation from date of diagnosis until they initiate the 1L therapy, and they are allowed up to 6 months to initiate first-line therapy.*

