7.2 STATISTICAL ANALYSES

7.3 ANALYSES FOR PRIMARY OBJECTIVE

For the primary objective, the association between primary independent variable (treatment type: palbociclib + AI or AI alone) and the outcome variable (OS) will be assessed using unadjusted Kaplan-Meier analysis and multivariable methods. The primary method of analysis to account for observed confounders will be stabilized inverse probability of treatment weighting (sIPTW). Additionally, as sensitivity analyses, multivariable Cox proportional hazards (CPH) regression and propensity score matching (PSM) will be performed. *Both IPTW and PSM are propensity score (PS)-based methods commonly used to achieve balance between treatment and control groups in retrospective cohort study designs.* All methods are described below in detail.

Kaplan-Meier Analysis

Time-to-event outcome (i.e., OS) will be described using unadjusted Kaplan-Meier analyses; median time-to-event (in months) and landmark probabilities of event at various timepoints (e.g., 12 months, 24 months) will be estimated, along with 95% CIs and log-rank *P* values. Graphical displays of the data will also be generated as appropriate. Kaplan-Meier analysis may also be performed using the stabilized weights or among the PS-matched groups (see details in this section below), and the weighted or PS-matched survival curves may be drawn.

Cox Proportional Hazards Regression

The CPH regression model may be used to estimate a hazard ratio of the OS, along with 95% CI, for the primary exposure—a dichotomous variable indicating whether the patient received AI + palbociclib versus AI alone—and for each of the control variables included in the model, indicating higher or lower rate of death (relative to a reference category) at any given point in time after the index date. The patient demographic and clinical characteristics that will be considered for confounding adjustment in the model are described earlier in [Table 5-2](#).

Propensity Score Estimation

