As the first step in implementation of PS-based methods (IPTW and PSM), the PS (i.e., the estimated probability of treatment assignment) will be obtained from a logistic regression model where the treatment assignment (treatment vs. control) will be regressed on a set of covariates or confounders. The baseline covariates or control variables that will be considered for adjustment in the multivariable logistic regression for deriving treatment probabilities (i.e., PSs for IPTW and PSM) are described earlier in [Table 5-2](#). The following variables will be included in the model: age group, race, year of mBC diagnosis, marital status, geographic status of residence, median household income, LIS coverage, tumor grade at initial diagnosis, involvement of metastatic sites at initial diagnosis (bone, brain, liver, and lung as independent binary variables), and NCICI score category. If any covariates are identified to have missing data, they may be coded as “missing” or “unknown” and included as categorical variables in the model.

Covariate Balancing

The following process will be implemented to determine whether there is sufficient overlap between the patient populations of the 2 treatment cohorts:

- Compute the standardized mean difference in PS for each level of each baseline covariate
- Graphically assess differences in the full distribution of each covariate between 2 treatment cohorts
- An absolute standardized mean difference < 0.1 indicates negligible difference and is considered a good balance

Covariate balance will be examined using both IPTW and PSM techniques as described below. Subsequently, depending on the quality of balance, the endpoint (OS) may be assessed using one or both techniques (Austin, 2014; Buchanan et al., 2014).

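### Individual ER and PR status are left out of the propensity model, the Cox covariates and the balance checks, so a difference in receptor pattern between arms would be neither balanced nor seen.

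*SAP*

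**What the plan says.** SAP section 7.3 states: "The primary method of analysis to account for observed confounders will be stabilized inverse probability of treatment weighting (sIPTW"). The primary OS hazard ratio therefore depends on what the propensity model contains. The list opens with "The following variables will be included in the model: age group, race, year of mBC diagnosis, marital status". It continues with geographic status, household income, low-income subsidy and tumor grade, and ends with "involvement of metastatic sites at initial diagnosis (bone, brain, liver, and lung as independent binary variables), and NCICI score category". Protocol section 9.7.1 leaves the final choice of variables to the SAP, so this list is the operative one.

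Both documents describe what SEER records for each reported diagnosis. SAP section 2.1 lists "clinical data about the tumor (e.g., stage, grade, size, estrogen receptor [ER] status, progesterone receptor [PR] status, and HER2 status"), and Protocol section 9.4 lists "clinical data about the tumor (e.g., stage, grade, size, ER status, PR status, and HER2 status), and cause and date of death".

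Receptor eligibility (SAP section 4.1, criterion 5) is "HR+/HER2- molecular subtype at diagnosis, using the SEER breast subtype variable (defined according to ER/PR and HER2 status"). No criterion asks for both receptors to be positive. Men and women are both eligible: "The study population will represent Medicare beneficiaries (men or women").

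Neither SAP Table 5-2 nor Protocol Table 1 defines a variable for ER status, PR status, tumor size or sex. No reason is given. The one variable that Table 5-2 expressly keeps out of the propensity model is Medicaid eligibility.

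**The concern.** Receptor pattern is a baseline tumor characteristic, recorded at diagnosis and so before first-line treatment begins. If it influences both the choice between palbociclib + AI and AI alone and survival on endocrine therapy, it is a confounder, and one that the data source is said to hold. In the limitations section (9.9) the protocol undertakes to adjust for risk factors that the database shows. Its examples of what cannot be seen are performance status, laboratory results and mutations, and receptor status is not among them.

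Within the combined subtype, one arm could hold more single-positive tumors than the other without any planned table showing it. Agreement between sIPTW, PSM and Cox regression would give no reassurance, because all three draw on the same covariate definitions. The study tests superiority on OS (SAP section 3). The first-line randomized trial cited in SAP section 2 reported a hazard ratio of 0.956, which is 4.4% from 1, so a systematic shift of a few percent deserves attention.

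**Working it through.** **Step 1. Is receptor status handled anywhere?** The documents state no sample size, event count or receptor distribution, so there is no figure of the plan's own to reproduce. Going through the analysis steps in SAP section 7.3:

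- *Propensity model (used by sIPTW and PSM):* closed list, without ER or PR.
- *Multivariable Cox model:* covariates taken from Table 5-2, without ER or PR.
- *Balance check:* standardized mean differences (SMDs) for each baseline covariate. ER and PR are not defined as covariates, so they are not checked.
- *Adjustment for residual imbalance after weighting:* optional, and dependent on the balance check, so it would not be triggered.
- *Other sensitivity analyses (section 7.6):* treatment start within 3 months, crossover adjustment and a different censoring rule. None concerns receptor status.

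The gap runs through every planned analysis of the primary objective.

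**Step 2. How much could it matter?** This uses the standard bias factor for an omitted binary confounder:

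factor = [1 + p1(h − 1)] / [1 + p0(h − 1)]

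Here p1 and p0 are the PR-negative proportions in the palbociclib + AI and AI-alone arms, and h is the hazard ratio for death of PR-negative against PR-positive tumors. The documents give none of these. The assumptions are a mean prevalence of 18%, a difference of 3, 6 or 10 points, and h of 1.3, 1.5 or 1.7. SMD = |p1 − p0| / √{[p1(1 − p1) + p0(1 − p0)]/2}.

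| p1 vs p0 | SMD | h = 1.3 | h = 1.5 | h = 1.7 |
|---|---|---|---|---|
| 16.5% vs 19.5% | 0.08 | 0.992 | 0.986 | 0.982 |
| 15% vs 21% | 0.16 | 0.983 | 0.973 | 0.963 |
| 13% vs 23% | 0.26 | 0.972 | 0.955 | 0.940 |

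Middle case: (1 + 0.15 × 0.5)/(1 + 0.21 × 0.5) = 1.075/1.105 = 0.973. Extreme corner: (1 + 0.13 × 0.7)/(1 + 0.23 × 0.7) = 1.091/1.161 = 0.940.

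With the arms reversed, the factors are the reciprocals: 1.028 in the middle case and 1.064 in the corner. With equal prevalence the factor is 1.000.

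**Step 3. Against the SAP's own standard.** The SAP treats an absolute SMD below 0.1 as negligible. A 3-point gap would pass (0.08). Gaps of 6 and 10 points would fail (0.16 and 0.26), but only if the variable were in the table.

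**Step 4. Sex.** With an assumed male share of 1% against 2% to 3% and a hazard ratio of 1.2 to 1.5, the same formula gives 0.990 to 0.998, a shift of at most about 1%.

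**The case against.** The strongest reply is that confounding is not shown. No passage says that receptor pattern influences the choice of first-line regimen or survival, and no ER/PR distribution by arm is given. The subtype definition does not spell out which ER/PR combinations count as HR+, so the presence of single-positive tumors is inferred from the absence of any criterion requiring both. The inputs in the working are assumptions, and the 6% end needs a 10-point gap together with a hazard ratio of 1.7. The formula also treats the imbalance as wholly uncorrected, whereas grade, metastatic sites, age and race are in the model and may balance part of it. All of this stands. It limits the size of the claim but does not explain why the variable is left out.

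A reader might go further and infer that tumor size and sex carry the same consequence. The documents do not support that. A difference in receptor biology follows from ER and PR only. Every patient is stage IV at diagnosis, and four metastatic sites are already in the model, so tumor size would need its own justification. Sex probably moves the hazard ratio by about 1% or less.

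A reader might also infer that adding the variables costs nothing. SAP section 7.3 itself warns of extreme weights and inflated variance. Sparse categories can make weights more variable or lose matches under the 0.01 caliper. Nor do the documents show that the fields are in the extract received: sections 2.1 (SAP) and 9.4 (Protocol) describe SEER content in general terms, data are released on application for what the study needs, and completeness is not stated.

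**Conclusion.** The omission of individual ER and PR status is real, unexplained and common to the primary sIPTW analysis and both alternative methods. If the arms differ on receptor pattern, nothing in the plan would balance or reveal it.

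The documents do not support saying that the arms do differ, or that the primary hazard ratio is biased towards palbociclib. Imbalance and direction are both unknown. On the assumed inputs the shift is about 1% to 6% either way and about 3% in the middle case, before allowing for partial balance through grade and the other covariates. The point is a moderate one and should be settled in the SAP before the final analysis. Sex and tumor size are secondary: they belong in the baseline and balance tables, with no presumption that they must enter the model.

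**What to change.** 1. In SAP Table 5-2, define ER/PR pattern at diagnosis as ER+/PR+, single-positive, or unknown.
2. Add it to the section 7.3 propensity list, to the covariates of the multivariable Cox model and to the SMD balance table. Collapse sparse levels as section 5.5 already permits. Keep unknown as a level, as section 7.3 already allows for missing covariate data.
3. Define sex and tumor size category (with unknown) in Table 5-2 and report their SMDs before and after weighting and matching. Put them in the models only if counts and completeness allow.
4. If ER/PR pattern is nevertheless left out, record the reason in the SAP and still report its SMD.

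The cost is SAP wording and modest programming, plus a check that the ER, PR and size fields are in the received extract and adequately complete. The statistical downside is small: somewhat more variable weights, or a few lost matches, where categories are sparse.

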## 9.9 Strengths and Limitations of Research Methods

This study is based on the analysis of the SEER-Medicare database—a database with a diverse array of demographic and clinical information on patients with incident diagnosis of cancer in the Medicare population in the US who are generally 65 years or older. The linkage of Medicare claims data with SEER registry data provides confirmatory data on cancer diagnoses along with precise dates, which in turn make it possible to attribute treatments as specific lines of therapy in alignment with their approved indications and guideline recommendations; this substantially minimizes the risk of misclassification—an inherent limitation in many other commonly used population-based administrative claims data sources in the US. The availability of up-to-date validated vital statistics data, as described in Section 9.4, further makes the database a unique and authoritative data resource for evaluation of survival outcomes in older patients with cancer, especially those represented in the US Medicare population.

There are certain limitations that are typically inherent in studies based on secondary data sources and are applicable to this current study as well:

PFIZER CONFIDENTIAL

- Patients are not randomized to treatment and control groups, and as such, the lack of random assignment may lead to selection bias. We plan to adjust for differences in baseline characteristics and risk factors that are observable in the database, but imbalances in many unobserved characteristics (e.g., performance status, laboratory test results, genetic mutations) may introduce unmeasured confounding.
- The US-labelled indication for palbociclib includes patients who were initially diagnosed at an earlier stage but later progressed to have advanced or metastatic disease; however, this analysis will be restricted to patients with de novo metastatic disease given limitation of the data source. This could potentially limit the generalizability of study findings beyond patients who are not diagnosed at the metastatic stage, but would be an appropriate approach in consideration of the fact that SEER does not collect information about progression or recurrences, and proxy methods to identify recurrences in the SEER-Medicare database are shown to have low sensitivity and specificity, especially among older patients (Hassett et al., 2014; Warren et al., 2016).

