The SEER-Medicare database is composed of 2 large population-based sources of data that provide detailed information about Medicare beneficiaries with cancer: (1) the SEER registry data that contain information about an incident cancer diagnosis and (2) linked Medicare data that contain longitudinal information on Medicare enrollment and

specific healthcare services received in different settings (e.g., hospitals, physician offices, outpatient clinics, nursing homes), as well as prescription drug utilization. The linkage of these 2 data sources results in a unique source of information that can be used for an array of epidemiological research, including health services use and survival outcomes, among older patients with cancer in the United States (US) Medicare population.

The SEER registries are part of the SEER Program, which is an epidemiologic surveillance system consisting of population-based tumor registries in certain states and metropolitan areas designed to track cancer incidence and survival in the US. The SEER registries collect information on nearly all (98%) newly diagnosed cancer cases, including breast cancer, in persons residing in SEER areas. SEER areas have been shown to be nationally representative (Nattinger et al., 1997) and the 21 registries represented in the SEER data linkage available for this study (SEER-21) capture over one-third (35%) of the total US population (Enewold et al., 2020). In contrast to the entire population of the US, the SEER Program encompasses a population that displays greater racial and ethnic diversity, along with a higher representation of individuals facing economic disadvantages (Enewold et al., 2020).

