3 HYPOTHESES AND DECISION RULES

The primary objective of this study is to demonstrate superiority of palbociclib + AI over AI monotherapy in prolonging OS for women and men aged ≥ 65 years with HR+/HER2- mBC as 1L treatment in the US clinical practice setting. The study is designed to test the null hypothesis $H_0: \lambda \geq 1$ versus alternative hypothesis $H_a: \lambda < 1$, palbociclib + AI cohort vs. AI monotherapy cohort, where λ stands for the hazard ratio.

PFIZER CONFIDENTIAL

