Metastatic site involvement at diagnosis	Clinical characteristic (assessed at mBC diagnosis)	The SEER-defined metastatic site variables will be used to describe involvement of any of the following sites at diagnosis: 
 • Bone • Brain • Liver • Lung • An additional variable will be created to describe presence of visceral metastases using the composite of liver and lung.
NCI Comorbidity Index (NCICI) Score	Clinical characteristic (assessed within the 6 months period before index date)	The comorbidity burden during the 6-month baseline period will be assessed using the NCI's comorbidity index, which is described in the Klabunde adaptation of the Charlson Comorbidity Index, version 2021 (Klabunde et al., 2007; National Cancer Institute, 2023a). NCICI scores will be reported as continuous and categorical variables: 
 • Score 0 • $0 < \text{Score} \leq 1$ • $\text{Score} > 1$

PFIZER CONFIDENTIAL

CT24-WI-GL03-RF03 2.0 Non-Interventional Statistical Analysis Plan For Secondary Data Collection Study
 01-Jun-2020
 Page 13 of 29

Variable	Role/objective	Definition
		
The specific comorbidities represented in the NCICI include the following:
 
 • Acute myocardial infarction • History of myocardial infarction • Congestive heart failure • Peripheral vascular disease • Cerebrovascular disease • Chronic obstructive pulmonary disease • Dementia • Paralysis (hemiplegia or paraplegia) • Diabetes without complications • Diabetes with complications • Renal disease • Mild liver disease • Moderate/severe liver disease • Peptic ulcer disease • Rheumatologic disease • AIDS
Age	Demographics (assessed at mBC diagnosis and at index date)	
Age at diagnosis will be assessed as continuous and categorical variables:
 
 • 65-69 years • 70-74 years • 75-79 years • ≥ 80 years
Year of diagnosis	Demographics (assessed at mBC diagnosis)	
Year of de novo mBC diagnosis will be described as a categorical variable:
 
 • 2015 • 2016 • 2017 • 2018 • 2019

PFIZER CONFIDENTIAL

Variable	Role/objective	Definition

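### The primary propensity score has no direct measure of functional status or recent acute care beyond a three-level comorbidity category, although the baseline claims appear able to supply proxies

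*SAP*

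**What the plan says.** SAP 3 sets the aim: "The primary objective of this study is to demonstrate superiority of palbociclib + AI over AI monotherapy in prolonging OS". SAP 7.3 names the method: "The primary method of analysis to account for observed confounders will be stabilized inverse probability of treatment weighting (sIPTW").

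Under Propensity Score Estimation, SAP 7.3 then lists what the model will contain. Demographic and area variables, LIS, year of diagnosis and grade come at the start. The remaining items cover disease spread and comorbidity: "involvement of metastatic sites at initial diagnosis (bone, brain, liver, and lung as independent binary variables), and NCICI score category". Table 5-2, the pool from which covariates may be drawn, has no admission, nursing-facility, home-health or frailty variable either.

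The general health measure is the comorbidity index: "The comorbidity burden during the 6-month baseline period will be assessed using the NCI's comorbidity index". It enters in three categories (0; above 0 to 1; above 1).

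Protocol 9.9 concedes that "imbalances in many unobserved characteristics (e.g., performance status, laboratory test results, genetic mutations) may introduce unmeasured confounding". SAP 2.1 describes the linked Medicare data as holding "specific healthcare services received in different settings (e.g., hospitals, physician offices, outpatient clinics, nursing homes"), and protocol 9.4 says the same. The baseline window is "The 6-month period before the study index date (to assess patient baseline demographic and clinical characteristics"). Inclusion criterion 8 requires Parts A and B with no HMO participation for at least 6 months before index.

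**The concern.** Weighting balances only what is in the model, and the balance check in SAP 7.3 (absolute standardized difference below 0.1) looks only at listed covariates. Two patients of the same age group, disease pattern and NCICI category can differ greatly in function. One may be a well outpatient, the other recently discharged from hospital to a nursing facility. The listed variables do not separate them on that difference.

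The endpoint is death from any cause in patients aged 65 or over, and the hypothesis runs in one direction (hazard ratio below 1). If poor function makes AI alone more likely and also raises mortality, the omission pushes the estimate in the direction the study hopes to show.

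The planned robustness checks would not reveal this. Multivariable Cox and PSM use the same covariates, so agreement among the three methods could be read as robustness that it does not establish. The other analyses in SAP 7.6 (3-month initiation subset, RPSFT, changed end of follow-up) answer different questions. None adds a measure of function or quantifies unmeasured confounding.

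**Working it through.** **Plan's own figure.** There is none to reproduce. Protocol 9.5 gives no sample size, and neither document gives an event count, a significance level or the prevalence of poor function. Everything below therefore rests on stated assumptions.

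**Step 1: bias from one omitted binary factor.** Let p1 and p0 be the shares with poor status on palbociclib + AI and on AI alone that remain after weighting, and R the mortality hazard ratio for poor status. At a true hazard ratio of 1, the estimate is approximately

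(1 + p1(R − 1)) / (1 + p0(R − 1)).

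Assumed ranges: p0 20-30%, p1 10-15%, R 1.5-2.5.

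| p0 | p1 | R | Calculation | Estimated HR |
|---|---|---|---|---|
| 20% | 15% | 1.5 | 1.075 / 1.10 | 0.977 |
| 20% | 10% | 1.5 | 1.05 / 1.10 | 0.955 |
| 30% | 15% | 2.0 | 1.15 / 1.30 | 0.885 |
| 30% | 15% | 2.5 | 1.225 / 1.45 | 0.845 |
| 30% | 10% | 2.5 | 1.15 / 1.45 | 0.793 |

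The assumed ranges thus span about 0.79 to 0.98.

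**Step 2: check against a Cox model.** The simulation used 60,000 patients, a true hazard ratio of 1, a median of 43.2 months for patients without poor status (the AI-alone median of the electronic-health-record study cited in SAP 2) and censoring spread over 6 to 70 months. For 30% vs 15% it gave 0.902 with R = 2 and 0.874 with R = 2.5. The formula gives 0.885 and 0.845, so it somewhat overstates the bias.

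**Step 3: consequence for the test.** Suppose bias alone produced a hazard ratio of 0.88, at an assumed one-sided 0.025. The chance of a significant result with no true effect is Φ(|ln 0.88| √(D·a(1 − a)) − 1.96), with D events and share a on palbociclib. For D = 300 this is 17% (a = 0.3) to 20% (a = 0.5). For D = 500 it is 26% to 30%. The event counts are assumed.

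**Step 4: what one proxy removes.** Take 30% vs 15%, R = 2, and one flag of assumed sensitivity 0.70 and specificity 0.85, standardised to equal-sized arms.

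- Flagged share: 0.15×0.70 + 0.85×0.15 = 0.2325 on palbociclib + AI; 0.30×0.70 + 0.70×0.15 = 0.315 on AI alone; average 0.27375.
- Poor status among flagged and unflagged: 0.105/0.2325 = 0.452 and 0.045/0.7675 = 0.059 on palbociclib + AI; 0.21/0.315 = 0.667 and 0.09/0.685 = 0.131 on AI alone.
- Standardised hazards: 1 + 0.27375×0.452 + 0.72625×0.059 = 1.166, and 1 + 0.27375×0.667 + 0.72625×0.131 = 1.278.
- Residual hazard ratio: 1.166/1.278 = 0.913, against 0.885 before. The share of log bias removed is 1 − ln 0.913/ln 0.885, about 25%.

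With sensitivity and specificity of 0.50/0.85 and 0.60/0.80 the residuals are 0.897 and 0.899, or about 11% and 13% removed.

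**The case against.** **The NCICI already reflects illness.** Its components include acute myocardial infarction, congestive heart failure, dementia and paralysis, assessed in the same 6 months. Age group and brain, liver and lung metastases are also in the model. This stands. A reader might infer that nothing in the propensity score reflects how ill or dependent the patient was, but Table 5-2 does not support that. What is missing is a direct measure beyond a coarse index.

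**The direction is not documented.** No section says that fitter patients receive palbociclib, and protocol 9.9 says only that imbalances may confound. This stands too. The listed covariates would absorb part of any such selection, so the bias may remain in part but is not shown to exist.

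**The limitation is disclosed, and unobserved selection is not ignored.** Initiation is limited to 6 months from diagnosis because later starters may differ in unobserved ways, and a 3-month subset may be run. But both restrict time to treatment in both arms and do not make the arms comparable on function. Protocol 9.9 also promises adjustment for risk factors observable in the database. Performance status is not observable there, but admissions and nursing-facility stays should be.

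**Availability is not proven.** The documents describe SEER-Medicare in general and do not list the claim files obtained. Home-health care is not among the settings they name. This stands and makes the fix conditional.

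**Proxies are weak.** Step 4 confirms that a single flag removes only a minority of the bias.

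**Baseline admissions may reflect the cancer diagnosis itself.** Some will. They still precede index and may affect both treatment choice and death, so they remain candidates for adjustment.

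**Conclusion.** The point holds in this form: the primary propensity score lacks a direct measure of function or recent acute care beyond the NCICI category, the baseline window and enrolment rule should make hospital and nursing-facility proxies obtainable, and no planned analysis fills the gap or sizes it. On assumed inputs the shift at a true hazard ratio of 1.00 is to about 0.79-0.98. This assumes that the imbalance is what remains after weighting; crude prevalences put into the same formula would overstate it.

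A reader might also take the contrast in the documents' own background, 0.956 in the randomised first-line trial against 0.55 to 0.76 in the observational studies, as evidence of this bias. The contrast is compatible with selection but does not prove it, because the populations differ. It does show that shifts of the size calculated here matter on the scale of interest.

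This is a worthwhile improvement to the plan, with medium confidence. It is neither an internal contradiction nor an arithmetical error.

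**What to change.** In SAP Table 5-2 and SAP 7.3, define two binary flags over the existing 6-month baseline period: any inpatient admission, and any skilled-nursing or nursing-home stay. Add a home-health flag if that file is held. Enter them in the propensity score, the multivariable Cox model and the balance table. Run the current covariate list as a sensitivity analysis and report both hazard ratios, so that the movement when the proxies enter is visible.

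The cost is SAP wording and a few derived variables, provided the relevant claim files are already held; no extra patients are needed. The propensity model becomes slightly larger and the weights somewhat more variable. Because the proxies capture only part of functional status, the limitation in protocol 9.9 should stay.
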